10.3.1 Study recording period and follow-up for adverse events and serious adverse events

Adverse events and serious adverse events will be recorded from time of signature of informed consent, throughout the treatment period and including the follow-up period (90 days after the last dose of durvalumab + tremelimumab).

During the course of the study all AEs and SAEs should be proactively followed up for each patient. Every effort should be made to obtain a resolution for all events, even if the events continue after discontinuation/study completion.

If a patient discontinues from treatment for reasons other than disease progression, and therefore continues to have tumor assessments, drug or procedure-related SAEs must be captured until the patient is considered to have confirmed PD and will have no further tumor assessments.

The investigator is responsible for following all SAEs until resolution, until the patient returns to baseline status, or until the condition has stabilized with the expectation that it will remain chronic, even if this extends beyond study participation.

10.3.2 Causality collection

The Investigator will assess causal relationship between the IPs and each AE and answer “yes” or “no” to the question “Do you consider that there is a reasonable possibility that the event may have been caused by the investigational product?”

For SAEs causal relationship will also be assessed for other medication and study procedures. Note that for SAEs that could be associated with any study procedure, the causal relationship is implied as “yes.”

A guide to the interpretation of the causality question is found in Appendix 1.

10.3.3 Relationship to protocol procedures

The Investigator is also required to provide an assessment of the relationship of SAEs to protocol procedures on the SAE report form. This includes both non-treatment-emergent (i.e., SAEs that occur prior to the administration of IP) and treatment-emergent SAEs. A protocol-related SAE may occur as a result of a procedure or intervention required during the study (e.g., blood collection). The following guidelines should be used by Investigators to assess the relationship of SAEs to the protocol:

- Protocol related: The event occurred due to a procedure or intervention that was described in the protocol for which there is no alternative etiology present in the patient’s medical record.

- Not protocol related: The event is related to an etiology other than the procedure or intervention that was described in the protocol. The alternative etiology must be documented in the study patient's medical record.

10.3.4 Expectedness

Unexpected AE: An AE, which varies in nature, intensity or frequency from information on the investigational drug/agent provided in the product IB, package insert or safety reports. Any AE that is not included in the IB, package insert, safety reports or informed consent is considered “unexpected”.

Expected (known) AE: An AE, which has been reported in the IB, package insert or safety reports. An AE is considered “expected”, only if it is included in the IB document as a risk.

10.3.5 Adverse events based on signs and symptoms

All AEs spontaneously reported by the patient or reported in response to the open question from the study personnel: “Have you had any health problems since the previous visit/you were last asked?” or revealed by observation will be collected and recorded in the eCRF. When collecting AEs, the recording of diagnoses is preferred, when possible, to recording a list of signs and symptoms. However, if a diagnosis is known and there are other signs or symptoms that are not generally part of the diagnosis, the diagnosis and each sign or symptom will be recorded separately.

10.3.6 Adverse events based on examinations and tests

The results from protocol-mandated laboratory tests and vital signs measurements will be summarized in the CSR. Deterioration as compared to baseline in protocol-mandated laboratory values and vital signs should therefore only be reported as AEs if they fulfill any of the SAE criteria or are the reason for discontinuation of treatment with the IPs.

If deterioration in a laboratory value or vital sign is associated with clinical signs and symptoms, the sign or symptom will be reported as an AE and the associated laboratory result or vital sign will be considered as additional information. Whenever possible, the reporting Investigator should use the clinical rather than the laboratory term (e.g., anemia versus low hemoglobin value). In the absence of clinical signs or symptoms, clinically relevant deteriorations in non-mandated parameters should be reported as AEs.

Deterioration of a laboratory value that is unequivocally due to disease progression should not be reported as an AE/SAE.

Any new or aggravated clinically relevant abnormal medical finding at a physical examination as compared with the baseline assessment will be reported as an AE.

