8.2.6 Clinical laboratory tests

Blood and urine samples for determination of clinical chemistry, hematology, and urinalysis will be taken at the times indicated in the assessment schedules and as clinically indicated (see **Table 2** through **Table 5**).

Clinical laboratory safety tests, including serum pregnancy tests, will be performed in a licensed clinical laboratory according to local standard procedures. Sample tubes and sample sizes may vary depending on the laboratory method used and routine practice at the site. Urine pregnancy tests may be performed at the site using a licensed test (urine or serum pregnancy test). Abnormal clinically significant laboratory results should be repeated as soon as possible (preferably within 24 to 48 hours).

Additional safety samples may be collected if clinically indicated at the discretion of the Investigator. The date, time of collection, and results (values, units, and reference ranges) will be recorded on the appropriate eCRF.

The laboratory variables to be measured are presented in **Table 4** (clinical chemistry), **Table 5** (hematology), and

Table 6 (urinalysis).

Other safety tests to be performed at screening include assessment for hepatitis B surface antigen, hepatitis C antibodies and HIV antibodies.

The following laboratory variables will be measured:

Table 4. Clinical chemistry and other miscellaneous labs

Albumin	^a	Tests for ALT, AST, alkaline phosphatase, and total bilirubin must be conducted and assessed concurrently. If total bilirubin is $\geq 2 \times$ upper limit of normal (and no evidence of Gilbert's syndrome) then fractionate into direct and indirect bilirubin.
Alkaline phosphatase ^a		
ALT ^a	^a	
Amylase ^b	^b	
AST ^a	^b	
Bicarbonate ^c	^b	
Bilirubin, total ^a	^b	
Calcium	^c	
Chloride ^c	^c	
Creatinine	^c	
Creatinine clearance ^c	^c	
Gamma glutamyltransferase ^c	^d	
Glucose	^d	
Lactate dehydrogenase	^d	
Lipase ^b	^d	
Magnesium ^c		
TSH		
T3, free ^d		
T4, free ^d		

Abbreviations: ALT Alanine aminotransferase; AST Aspartate aminotransferase, TSH Thyroid Stimulating Hormone

Table 5. Hematology

Absolute neutrophil count	
Hemoglobin	
Absolute lymphocyte count	
Platelet count	

Note: For coagulation parameters, activated partial thromboplastin time and international normalized ratio are to be assessed at baseline and as clinically indicated

Table 6. Urinalysis

Urinalysis should be done at baseline (screening) and then as clinically indicated

Bilirubin	
Blood	

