Color and appearance	
Glucose	
Ketones	
pH	
Protein	
Specific gravity	

Note: Microscopy should be used as appropriate to investigate white blood cells and use the high power field for red blood cells.

If a patient shows an AST or ALT $\geq 3 \times$ ULN together with total bilirubin $\geq 2 \times$ ULN, refer to **Appendix 1** for further instructions on cases of increases in liver biochemistry and evaluation of Hy's Law. These cases should be reported as SAEs if, after evaluation, they meet the criteria for a Hy's law case or if any of the individual liver test parameters fulfill any of the SAE criteria.

All patients should have further chemistry profiles performed at 30 days (± 3 days), 2 months (± 1 week) and 3 months (± 1 week) after permanent discontinuation of IP (see Study Schedule in Section 8).

Any clinically significant abnormal laboratory values should be repeated as clinically indicated and recorded on the eCRF. Situations in which laboratory safety results should be reported as AEs are described in Section 10.3.6.

All patients with Grade 3 or 4 laboratory values at the time of completion or discontinuation from IP must have further tests performed until the laboratory values have returned to Grade 1 or 2, unless these values are not likely to improve because of the underlying disease.

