10.1 Safety parameters

10.1.1 Definition of adverse events

An adverse event is the development of an undesirable medical condition (other than progression of the malignancy under evaluation) or the deterioration of a pre-existing medical condition following or during exposure to a pharmaceutical product, whether or not considered causally related to the product. An undesirable medical condition can be symptoms (e.g., nausea, chest pain), signs (e.g., tachycardia, enlarged liver) or the abnormal results of an investigation (e.g., laboratory findings, electrocardiogram). In clinical studies, an AE can include an undesirable medical condition occurring at any time, including run-in or washout periods, even if no study treatment has been administered.

The term AE is used to include both serious and non-serious AEs.

Laboratory abnormalities: Laboratory abnormalities present at the screening visit will be recorded as pre-treatment signs and symptoms. After study treatment administration, all grade 3 and 4 clinical laboratory results that represent an increase in severity from baseline will be reported as AEs. A grade 1 or 2 clinical laboratory abnormality should be reported as an AE only if it is considered clinically significant by the investigator (i.e. it induces clinical signs or symptoms or requires therapy).

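### Sections 10.1.1 and 10.3.6 disagree on whether some asymptomatic Grade 3–4 laboratory worsening is an AE, so such values may get no attribution and no row in the planned AE table

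*Combined protocol and SAP*

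**What the plan says.** Section 10.1.1 states, for the time after study treatment is given, that "all grade 3 and 4 clinical laboratory results that represent an increase in severity from baseline will be reported as AEs". It sets a narrower test for Grades 1 and 2, which become AEs only when the investigator judges them clinically significant.

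Section 10.3.6 starts from a different premise: "The results from protocol-mandated laboratory tests and vital signs measurements will be summarized in the CSR". It concludes that deterioration from baseline in those mandated tests "should therefore only be reported as AEs if they fulfill any of the SAE criteria or are the reason for discontinuation of treatment"; the treatment meant is the IPs. It makes no exception by CTCAE grade. If signs or symptoms accompany the change, the sign or symptom is the AE and the value is supporting information. Clinically relevant deterioration in tests that are not mandated is an AE even without symptoms. Two qualifiers follow: "Whenever possible, the reporting Investigator should use the clinical rather than the laboratory term", and "Deterioration of a laboratory value that is unequivocally due to disease progression should not be reported as an AE/SAE".

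Section 8.2.6, which governs the laboratory tests, says: "Situations in which laboratory safety results should be reported as AEs are described in Section 10.3.6". It does not mention 10.1.1.

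Section 11.2.1 plans to summarize safety as the share of patients with AEs, broken down by type, CTCAE v5.0 grade and attribution. Sections 10.3 and 10.3.2 collect the yes/no causality rating against the IPs for each AE.

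**The concern.** Safety of the combination is the only secondary objective in section 2.2, and the AE table in 11.2.1 is its planned summary. If two investigators, or one investigator at two times, can follow different sections and enter different events, the Grade 3–4 laboratory rows have no single meaning. The laboratory section points to the restrictive rule, so that may well be the one used in practice, contrary to the definition section. A value not entered as an AE receives no causality rating, and attribution is harder to assign reliably later.

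**Working it through.** There is no stated figure to reproduce. The check is a comparison of the two rules, followed by the weight of one patient in a table row.

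**1. The two rules applied to a Grade 3–4 worsening of a protocol-mandated laboratory value**

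| Situation | 10.1.1 | 10.3.6 |
|---|---|---|
| Meets an SAE criterion | AE | AE |
| Is the reason for stopping the IPs | AE | AE |
| Comes with signs or symptoms | AE | The sign or symptom is the AE |
| None of these | AE | Not an AE |

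Only the last line is a direct contradiction. Neither section says which prevails, and nothing visible elsewhere does. It is confined to mandated tests, because 10.3.6 reports clinically relevant changes in other tests. In the study schedule the chemistry panel and blood count recur through treatment, so routine on-study tests are covered. Amylase, lipase, LDH, GGT and magnesium appear at screening only in the schedule as extracted, so later values of these may fall outside.

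**2. What is captured anyway**

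- Section 10.1.3 lists transaminase, creatinine, lipase and amylase increases, and other potentially immune-mediated events, as AESIs whether serious or not.
- Sections 8.2.6 and 10.3.7 give a Hy's law route to SAE reporting.
- Section 8.2.1 makes worsening of a condition already present at baseline an AE.

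The disputed class is what remains after these routes.

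**3. Consequence for the table**

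No AE entry means no causality rating (10.3, 10.3.2), and hence no contribution to a table of AEs by attribution (11.2.1). The value still reaches the CSR laboratory summary, for which neither grade nor attribution is specified.

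**4. Size**

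Let k be the number of patients whose only Grade 3–4 event of one laboratory type is in the disputed class, and N the number in the safety set. The difference between the rules in that row is k/N. The documents give no value for k, so it is assumed here. Section 11.3 gives 20 evaluable and 22 enrolled patients.

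| k | N = 20 | N = 22 |
|---|---|---|
| 0 | 0 | 0 |
| 1 | 1/20 = 5.0 points | 1/22 = 4.5 points |
| 2 | 2/20 = 10.0 points | 2/22 = 9.1 points |
| 3 | 3/20 = 15.0 points | 3/22 = 13.6 points |

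If the trial stops after the 8 evaluable patients of stage one, and the safety set is also 8, one patient is 1/8 = 12.5 points. Patients treated but not evaluable would enlarge N and reduce that weight.

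**5. The separate safety-set mismatch**

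The synopsis requires DEB-TACE and at least one dose of either drug. Section 11.1.1 accepts any study treatment, DEB-TACE included. A patient who had DEB-TACE only, for instance one replaced under section 4.4 after medical complications, is in the second set and not the first.

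**The case against.** The strongest reply is that little is lost. The AESI, Hy's law and pre-existing-condition routes take many of the important abnormalities. What remains is non-serious, asymptomatic and did not stop treatment. The values are still collected and summarized, the safety analysis is descriptive, and no decision rule uses the AE table. For non-serious AEs, section 10.3 rates causality against the IPs only, so attribution to DEB-TACE would not be gained under either rule. All of this stands and limits the point to a reporting inconsistency. It does not remove the contradiction.

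Reading 10.1.1 as the general rule and 10.3.6 as the specific one does not settle the matter, because the laboratory paragraph in 10.1.1 is itself specific and separates Grades 3–4 from Grades 1–2.

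Two stronger readings are tempting and are not supported:

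- *That the run-in count changes.* Section 6.3 counts most non-immune events of Grade 3 or higher, so a reader might infer that an unreported laboratory AE escapes the count. But its transaminase and bilirubin criterion is written on the value itself, and it provides for repeat testing to confirm laboratory findings before they are designated as unacceptable toxicities. Both point away from dependence on AE entry. Several laboratory abnormalities are excluded under stated conditions, and part of the surrounding text is not visible.
- *That an asymptomatic Grade 3 hemoglobin fall has no route to an AE.* Entry is allowed down to 9.0 g/dL, so anemia present at baseline that worsens can be an AE under 8.2.1. Section 10.3.6 also uses anemia as its example of a preferred clinical term. That example follows text on signs and symptoms, so it does not decide the asymptomatic case, but it makes hemoglobin a poor proof.

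**Conclusion.** The contradiction is certain from the text; its effect on the results is not. For the residual class defined above, following 10.3.6 removes events from the AE table and leaves them without attribution, while 10.1.1 keeps them. The size is about 5 points in one row per affected patient at N = 20 to 22, more after a stage-one stop, with the number of such patients unknown and possibly 0. What is at risk is attribution and a single meaning of the table, not the underlying data. ORR and the Simon design do not depend on this, and no run-in effect is shown. It should be corrected before the AE table is produced. The safety-set mismatch is a smaller, independent correction and adds no weight to the main point.

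**What to change.** Reconcile 10.1.1 and 10.3.6 into one rule for laboratory AEs and have 8.2.6 cite it. There are two coherent choices:

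- **Keep 10.1.1.** Record Grade 3–4 worsening from baseline as an AE with attribution. This fits 11.2.1 best. Retain from 10.3.6 the exception for deterioration clearly due to disease progression and the preference for clinical terms.
- **Keep 10.3.6.** Correct 10.1.1, tabulate worst on-study CTCAE laboratory grade from values already collected, and state in 11.2.1 that these values carry no attribution. Section 8.2.6 already works with laboratory grades: "All patients with Grade 3 or 4 laboratory values at the time of completion or discontinuation from IP must have further tests performed".

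Align the synopsis safety population with 11.1.1, so that patients who received only DEB-TACE are included.

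The cost is wording, and no new tests or visits. The first choice adds AE entries with their dates, action, outcome and causality fields, in a number that cannot be estimated from the documents. The protocol is at version 11.0, so patients may already have been treated, though the documents do not say. For any such patients, the first choice needs back-entry from stored values, or a statement of the date on which the rule changed. The second choice adds one table.

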10.3.7 Hy's Law

Cases where a patient shows elevations in liver biochemistry may require further evaluation and occurrences of AST or ALT $\geq 3 \times$ ULN together with total bilirubin $\geq 2 \times$ ULN may need to be reported as SAEs. This precludes the week following DEB-TACE. Please refer to Appendix 1 for further instruction on cases of increases in liver biochemistry and evaluation of Hy's law.

10.3.8 Disease progression

Disease progression can be considered as a worsening of a patient's condition attributable to the disease for which the IP is being studied. It may be an increase in the severity of the disease under study and/or increases in the symptoms of the disease. The development of new or progression of existing metastasis to the primary cancer under study should be considered as disease progression and not an AE. Events that are unequivocally due to disease progression should not be reported as an AE during the study.

10.3.9 New cancers

The development of a new cancer should be regarded as an SAE. New primary cancers are those that are not the primary reason for the administration of the IP and have been identified after the patient's inclusion in this study.

10.3.10 Deaths

All deaths that occur during the study treatment period, or within the protocol-defined follow-up period after the administration of the last dose of study drug, must be reported as an SAE

Deaths occurring after the protocol defined safety follow up period after the administration of the last dose of study drug should be documented in the eCRF. If the death occurred as a result of an event that started after the defined safety follow up period and the event is considered to be due to a late onset toxicity to study drug, then it should also be reported as an SAE.

AstraZeneca/MedImmune retains the right to request additional information for any patient with ongoing AE(s)/SAE(s) at the end of the study, if judged necessary.

10.3.11 Reporting of serious adverse events

All SAEs (including deaths) occurring from time of signature of informed consent through 90 days after the last dose of durvalumab or until the initiation of alternative anticancer therapy will be collected and reported.

SAEs will be reported promptly to the IND Sponsor and AstraZeneca within 24 hours of initial notification of the SAE. If this falls on a weekend or holiday, an email notification is acceptable but must be followed by an SAE reporting form on the next business day.

SAE reports and any other relevant safety information are to be sent to:

A **cover page** should accompany the **SAE** form when submitting to AstraZeneca indicating the following:

- “Notification from an Investigator Sponsored Study”
- The investigator IND number assigned by the FDA
- The investigator's name and address
- The trial name/title and AstraZeneca ISS reference number (ESR-17-12965)

- Sponsor must also indicate, either in the SAE report or the cover page, the **causality** of events **in relation to all study medications** and if the SAE is **related to disease progression**, as determined by the principal investigator.

10.3.11.1 Follow-up of Adverse Events and Serious Adverse Events

After the initial AE or SAE report, the investigator is required to proactively follow each subject and provide further information to the safety department in regard to the subject's condition.

All AE(s) and SAE(s) will be followed until:

- Resolution
- The condition stabilizes
- The event is otherwise explained
- The subject is lost to follow-up
- Death

As soon as relevant information is available, a follow-up SAE report will be submitted to the IND Sponsor and AstraZeneca.

10.3.11.2 Institutional Review Board (IRB)

All serious adverse events will be reported to the IRB per institutional standards. Upon receipt, follow-up information will be given to the IRB (as soon as relevant information is available) per institutional standards.

10.3.11.3 Food and Drug Administration (FDA)

All reporting to the FDA will be completed by the IND Sponsor.

Expedited IND Safety Reports

7 Calendar-Day Telephone or Fax Report:

The IND Sponsor is required to notify the FDA of any fatal or life-threatening adverse event that is unexpected and assessed by the investigator to be possibly related to the investigational agent. Such reports are to be telephoned or faxed [contact]) to the FDA within 7 calendar days of first learning of the event. Follow-up information will be submitted to the FDA as soon as relevant information is available.

15 Calendar-Day Written Report:

The IND Sponsor is required to notify the FDA of any SAE that is unexpected and related to the investigational agent in a written IND Safety Report.

Written IND Safety Reports should include an Analysis of Similar Events in accordance with regulation 21 CFR § 312.32. All safety reports previously filed with the IND concerning

similar events should be analyzed. The new report should contain comments on the significance of the new event in light of the previous, similar reports.

Written IND safety reports with Analysis of Similar Events are to be submitted to the FDA within 15 calendar days of first learning of the event. Follow-up information will be submitted to the FDA as soon as relevant information is available.

IND Annual Reports

In accordance with the regulation 21 CFR § 312.33, the IND Sponsor shall within 60 days of the anniversary date that the IND went into effect submit a brief report of the adverse events and progress of the investigation. Please refer to Code of Federal Regulations, 21 CFR § 312.33 for a list of the elements required for the annual report. All IND annual reports will be submitted to the FDA by the IND Sponsor.

